9.8.2 Rash

Individuals who develop a generalized rash will be monitored closely. Study drug dosing should be interrupted if a subject develops a generalized rash of Grade 3 or higher (Section 13.1.1.4), or a rash that is considered a serious adverse event (SAE). The investigator will notify the medical monitor of any rash that results in interruption of study drug, is Grade 3 or higher, or is an SAE. Investigators should consider additional evaluation including laboratory testing (e.g., complete blood count with differential, liver function tests), photographs of the rash, and dermatology consultation. The investigator may consider resumption of study drug if considered clinically appropriate.

9.9 Removal of Subjects

Subjects may withdraw from the study at any time at their own request. Subjects may be withdrawn from study drug treatment at any time at the discretion of the investigator or Vertex for safety, behavior, noncompliance with study procedures, or administrative reasons.

In addition, a subject must be discontinued from study drug treatment if the subject meets any of the following criteria:

- Meets any of the stopping (discontinuation) criteria (Section 9.8)
- Becomes pregnant (Section 11.5.6.2)

If a subject does not return for a scheduled visit, reasonable effort will be made to contact the subject. In any circumstance, reasonable effort will be made to document subject outcome. The investigator will inquire about the reason for withdrawal, request that the subject return all unused investigational product(s), request that the subject return for an ETT Visit and Safety Follow-up Visit, if applicable (see Section 9.1.2), and follow up with the subject regarding any unresolved AEs.

If the subject withdraws consent or assent for the study, no further assessments will be performed. Vertex may retain and continue using the study data and samples after the study is over, and may use the samples and information in the development of the study compounds, and for other drugs and diagnostics, in publications and presentations, and for education purposes. If the subject withdraws from the study, the study data and samples collected will remain part of the study. A subject will not be able to request the withdrawal of his or her information from the study data. A subject may request destruction of the samples collected from him or her during the study as long as those samples can be identified as his or her samples.

9.10 Replacement of Subjects

Subjects who withdraw or are withdrawn during the study drug Treatment Period will not be replaced.

10 STUDY DRUG INFORMATION AND MANAGEMENT

Study drug refers to VX-445/TEZ/IVA and IVA.

10.1 Preparation and Dispensing

Study drug may be dispensed only under the supervision of the investigator or an authorized designee and only for administration to the study subjects.

10.2 Packaging and Labeling

Study drug tablets will be supplied in blister cards by Vertex. Study drug labeling will be in compliance with applicable local and national regulations. Additional details regarding packaging, labeling, and dispensing for study drug will be in the Pharmacy Manual.

10.3 Study Drug Supply, Storage, and Handling

Study drug will be supplied as film-coated tablets (Table 10-1). The investigator, or an authorized designee (e.g., a licensed pharmacist), will ensure that all investigational product is stored in a secured area, under recommended storage conditions, and in accordance with

applicable regulatory requirements. Detailed instructions regarding the storage, handling, and dispensation of the study drug will be provided in the Pharmacy Manual.

Table 10-1 Study Drug: Dosing Form/Route/Strength

Drug Name, Dosing Form, Route	Tablet Strength (Subjects ≥12 Years or ≥30 kg)	Tablet Strength (Subjects <12 Years and <30 kg)
VX-445/TEZ/IVA, FDC tablet, oral		
VX-445	100 mg	50 mg
TEZ	50 mg	25 mg
IVA	75 mg	37.5 mg
IVA, tablet, oral	150 mg	75 mg

FDC: fixed-dose combination; IVA: ivacaftor; TEZ: tezacaftor

10.4 Drug Accountability

The pharmacist or designated study site staff will maintain information about the dates and amounts of (1) study drug received; (2) study drug dispensed to the subjects; and (3) study drug returned by the subjects. Subjects will be instructed to return all used and unused materials associated with the study drug to the site. These materials will be retained at the site according to instructions provided by Vertex or its designee. The study monitor will review study drug records and inventory throughout the study. If a site uses a site-specific drug accountability system and/or process, including processes associated with the destruction of returned materials, the process must be documented and approved by Vertex. The study monitor must review the drug accountability documentation on a regular basis. The study monitor will promptly communicate to Vertex any discrepancies he or she is unable to resolve with the site.

10.5 Disposal, Return, or Retention of Unused Drug

The study site staff or pharmacy personnel will retain all materials returned by the subjects until the study monitor has performed drug accountability. The investigator will ensure that the materials are destroyed in compliance with applicable environmental regulations, institutional policy, and any special instructions provided by Vertex. Destruction will be adequately documented.

10.6 Compliance

To ensure treatment compliance, the investigator or designee will supervise all study drug dosing that occurs at the site. At each visit, site personnel will review that the subject is compliant with study drug dosing and remind the subject of study drug dosing requirements. Compliance will also be assessed by ongoing study drug count.

If a subject demonstrates continued noncompliance of study drug dosing despite educational efforts, the investigator should consider discontinuing the subject from the study.

10.7 Blinding and Unblinding

This will be an open-label study; however, subjects and their legally appointed and authorized representative (e.g., parent or legal guardian) should not be informed of their study-related spirometry and LCI, SwCl, FE-1, and IRT results until the study has been completed, regardless if the subject permanently discontinues treatment. In addition, the Vertex study team will not

have access to the spirometry, LCI, or SwCl results of the present study until the database lock of the parent study.

11 ASSESSMENTS

The schedule of assessments is shown in [Table 3-1](#) and [Table 3-2](#).

11.1 Subject and Disease Characteristics

Subject and disease characteristics include the following: demographics, medical history, height, and weight. Select demographic and medical history will be derived from the parent study.

11.2 Pharmacokinetics

Not applicable.

11.3 Efficacy and Pharmacodynamics

11.3.1 Spirometry

Spirometry will be performed according to the American Thoracic Society Guidelines¹⁵ and according to the additional guidelines that follow.

Pre-bronchodilator spirometry is defined as spirometry testing performed for subjects who have

- withheld their short-acting bronchodilators (e.g., albuterol) or anticholinergic (e.g., ipratropium bromide [Atrovent[®]]) for more than 4 hours before the spirometry assessment;
- withheld their long-acting bronchodilator (e.g., salmeterol) for more than 12 hours before the spirometry assessment; and
- withheld their once-daily, long-acting bronchodilator (e.g., tiotropium bromide [Spiriva[®]]) for more than 24 hours before the spirometry assessment.

At all visits, all spirometry assessments should be performed pre-bronchodilator. During the Treatment Periods, spirometry assessments must be performed before study drug dosing (Section [9.6.1](#)) at approximately the same time at each visit. In the event that a subject forgets to withhold bronchodilator(s), spirometry should be performed according to the following:

- If a subject's Part A Day 1 spirometry assessment is pre-bronchodilator, but, on a subsequent visit, the subject forgets to withhold bronchodilator use, a post-bronchodilator spirometry assessment will be obtained for that visit only, and the visit will not be rescheduled.
- If, on Part A Day 1, the subject forgets to withhold his or her dose of bronchodilator, spirometry should be performed post-bronchodilator, and all subsequent spirometric measurements (according to the schedule of assessments) should be performed post-bronchodilator.
- Each spirometry assessment will be recorded in the source documents as pre- or post-bronchodilator.

All sites will be provided with spirometers to be used for all study assessments. Spirometry data will be transmitted to a centralized spirometry service for quality review.

See Section [10.7](#) for information about access to spirometry results.

The measured spirometric values listed below will be converted to percent predicted values using the standard equations of Global Lung Function Initiative (GLI).¹⁶

- FEV₁ (L)
- Forced vital capacity (FVC) (L)
- FEV₁/FVC (ratio)
- Forced expiratory flow, midexpiratory phase (FEF_{25%-75%}) (L/s)

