- Information about bronchodilator use during the study will be collected and documented. Subjects who are using a bronchodilator should have their spirometry assessments performed according to the guidelines provided in Section [11.3.1](#).

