12.3 Statistical Analysis

12.3.1 General Considerations

Continuous variables will be summarized using the following descriptive summary statistics: the number of subjects (n), mean, SD, median, minimum value (min), and maximum value (max). The precision of the measurement for each continuous variable will be specified in the SAP. Unless otherwise specified, min and max values will be reported with the same precision as the units of the raw data. The mean, median, and SD will be reported to 1 additional decimal

place. Any values that require a transformation to standard units (metric or SI) will be converted with the appropriate precision.

Categorical variables will be summarized using counts and percentages. Percentages will be presented to 1 decimal place.

The baseline value, unless otherwise specified, will be the most recent non-missing measurement (scheduled or unscheduled) collected before the first dose of study drug in the parent study. For assessments collected in replicates, the baseline will be defined as the average of non-missing values.

Change (absolute change) from baseline will be calculated as post-baseline value – baseline value.

The **Efficacy Analysis Period** for each Part will include the time from the first dose of study drug to the last scheduled efficacy visit in the corresponding Part, unless otherwise specified.

The **Treatment-emergent (TE) Period** for each Part will include the time from the first dose of study drug to 28 days after the last dose of the study drug or to the date of completion of study participation in the corresponding Part (as defined in Section 9.1.5), whichever occurs first.

Part A and Part B data will be analyzed separately, using the respective analysis set, efficacy analysis period, and TE period for each Part. For analysis of the number of PEx, events in the parent study and this study (Parts A and B, as applicable) may also be combined.

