10 STATISTICAL ANALYSIS

10.1 General Considerations

The Schedule of Assessments is provided in Section 3 of the CSP. The precision standards for reporting safety and efficacy variables are provided in an internal Biometrics document that specifies the programming rules including the precision for derived variables.

Continuous variables will be summarized using the following descriptive summary statistics: the number of subjects (n), mean, standard deviation (SD), median, minimum value (min), and maximum value (max).

Categorical variables will be summarized using counts and percentages. Percentages will be presented to 1 decimal place.

Baseline unless otherwise specified, is defined as the most recent non-missing measurement (scheduled or unscheduled) collected prior to the first dose of study drug in the parent study.

Note: for subjects who take Orkambi or Symdeko (branded as Symkevi in Europe) during the 28 days before the screening visit, the data collected at screening visit will not be used for baseline derivation for spirometry, sweat chloride and LCI.

Absolute change from baseline will be calculated as Post-baseline value – Baseline value.

Relative change from baseline will be calculated and expressed in percentage as $100\% \times (\text{Post-baseline value} - \text{Baseline value}) / \text{Baseline value}$.

Unscheduled visits: Unscheduled visit measurements will be included in analysis as follows:

- In scheduled visit windows per specified visit windowing rules
- In the derivation of baseline and last on-treatment measurements
- In the derivation of maximum and minimum values during TE period, and maximum and minimum change from baseline values during TE period for safety analyses
- In individual subject data listings as appropriate

Visit windowing rules: The analysis visit windows for protocol-defined visits are provided in Appendix A.

Incomplete/missing data will not be imputed, unless specified otherwise.

Outliers: No formal statistical analyses will be performed to detect or remedy the presence of statistical outliers, unless specified otherwise.

Multiplicity: There will be no multiplicity adjustment as no hypothesis test is planned for safety analysis, unless specified otherwise.

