10.3.1.2.2 Analysis Method

Absolute change in ppFEV₁ from baseline:

In the MMRM for the OLE efficacy period for Part A, the absolute change from baseline in ppFEV₁ will be analyzed using the MMRM approach based on the OLE-FAS for Part A. The model will include absolute change from baseline in ppFEV₁ as the dependent variable, and visit as the fixed effect, with baseline ppFEV₁ value and genotype group (F/F vs. F/MF) as covariates. The model will be estimated using restricted maximum likelihood. Denominator degrees of freedom for the *F*-test of fixed effects will be estimated using the Kenward-Roger approximation². An unstructured covariance structure will be used to model the within-subject errors. If the model estimation does not converge, a compound symmetry covariance structure will be used instead. Conditional on the observed data and covariates, missing data will be assumed to be missing at random; consequently, no imputation of missing data will be performed.

The estimated mean change from baseline in ppFEV₁ at each post-baseline visit, along with the corresponding 2-sided 95% confidence interval (CI) will be provided.

The analysis will be conducted with the clinic spirometry data only. An additional analysis may also be performed to include pooled spirometry data obtained in clinic and by Air Next Spirometer, if the Air Next Spirometry data are assessed to be reasonably consistent with clinic spirometry data.

Absolute change in sweat chloride from baseline:

Analysis of this PD variable will be based on an MMRM similar to the analysis of the absolute change in ppFEV₁ from baseline with the baseline sweat chloride included as a covariate instead of baseline ppFEV₁.

Absolute change in the CFQ-R respiratory domain score from baseline:

Analysis of this domain (child's version) will be based on an MMRM similar to the analysis of the absolute change in ppFEV₁ from baseline with the baseline CFQ-R respiratory domain score (child's version) included as a covariate instead of baseline ppFEV₁. The analysis will include clinic assessed CFQ-R RD score only. An additional analysis may be performed to include pooled CFQ-R RD score assessed at clinic and at home, if the home assessed data are reasonably consistent with the clinic assessed data.

Absolute change in BMI and BMI-for-age z-score from baseline:

Absolute change in weight and weight-for-age z-score from baseline:

Absolute change in height and height-for-age z-score from baseline:

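### Does ignoring the pre-/post-bronchodilator state of spirometry tests undermine the ppFEV₁ change-from-baseline analysis?

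*Protocol*

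**What the plan says.** Protocol 11.3.1 sets the default: "At all visits, all spirometry assessments should be performed pre-bronchodilator". It then deals with two kinds of lapse.

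- **Lapse at a later visit**, after a pre-bronchodilator Part A Day 1: "a post-bronchodilator spirometry assessment will be obtained for that visit only, and the visit will not be rescheduled".
- **Lapse on Part A Day 1:** that test is done post-bronchodilator and "all subsequent spirometric measurements (according to the schedule of assessments) should be performed post-bronchodilator".

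The state is not lost. "Each spirometry assessment will be recorded in the source documents as pre- or post-bronchodilator", and Protocol 9.5 adds: "Information about bronchodilator use during the study will be collected and documented".

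The baseline for change is earlier than Part A Day 1. Protocol 12.3.1 takes "the most recent non-missing measurement (scheduled or unscheduled) collected before the first dose of study drug in the parent study", and SAP 10.1 repeats this. The one spirometry-specific exclusion in SAP 10.1 concerns screening values after recent use of certain CFTR modulators, not bronchodilator state.

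The ppFEV₁ models in SAP 10.3.1.2.2 (Part A) and 10.3.2.2.2 (Part B) have visit as fixed effect, with baseline ppFEV₁ and "genotype group (F/F vs. F/MF) as covariates". Clinic spirometry only is used in the main analysis. The visit-window notes in Appendix A and the spirometry handling rules in Appendix C do not mention bronchodilator state. The SAP's only bronchodilator items are prior-use baseline characteristics.

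Protocol 12.3.3.2 leaves ppFEV₁ sensitivity analyses to the SAP. SAP 10.3.1.2.3 and 10.3.2.2.3 declare them not applicable because the primary endpoints are safety and tolerability.

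**The concern.** The consistency rule is anchored to one test and the change score to another. A subject who forgets on Part A Day 1 is then tested post-bronchodilator at every later visit, but is compared with a value taken before the first parent-study dose, possibly pre-bronchodilator. A site that follows the protocol exactly could thus carry the mismatch through both Parts. One-off lapses add scattered mismatches.

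A post-bronchodilator test against a pre-bronchodilator baseline mixes the acute bronchodilator response into the reported long-term change and would be expected to push it upward. The reverse mismatch would push it downward. Neither the baseline covariate nor the missing-at-random assumption corrects for this, because neither carries test state. With no sensitivity analysis and no planned count of mismatched tests, a reader could not tell from the planned tables whether the ppFEV₁ estimate depends on them.

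**Working it through.** The plan has no figure to reproduce: enrolment is by rollover, with no power calculation. The check has two parts.

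**1. Can the Day 1 rule create a mismatch?**

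- Under Protocol Table 3-1 (footnote d) and 9.1.1, Part A Day 1 should fall on the day of the parent study's last scheduled visit. If it is within 1 day, assessments already specified for that visit are not repeated.
- By default, then, the Part A Day 1 spirometry is the parent study's final on-treatment test, done under the parent study's spirometry rule. Subjects who start more than 1 day later, or who enrol during a drug interruption, repeat the assessments.
- If the parent rule tied later tests to the state at its own Day 1, carrying the final state forward would tend to preserve agreement with baseline. If it did not, carrying it forward could break agreement.
- The parent rule is not in these documents, so neither can be asserted. Only the one-off lapse, against a pre-bronchodilator baseline, is a mismatch that can be inferred from this protocol alone.

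**2. How large could the effect be?**

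Inputs from the documents: n = 64 enrolled (SAP 7.2). Scheduled treatment-period spirometry after each Part's Day 1 (Protocol Tables 3-1 and 3-2) is 9 visits in Part A and 8 in Part B, so 17 per subject and at most 17 × 64 = 1,088 tests.

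Assumed inputs, which the documents do not give: k subjects mismatched, within-subject response d points, SD of change 8 to 12 points, one-off lapse rate 1% to 5%.

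*Shift in a visit mean* = (k up − k down) × d / 64

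| Case | Calculation | Shift (points) |
|---|---|---|
| Central, one direction | 3 × 5 / 64 | 0.23 |
| Mixed directions | (2 − 1) × 5 / 64 | 0.08 |
| Low end | 1 × 2 / 64 | 0.03 |
| High end | 6 × 10 / 64 | 0.94 |
| One-off lapses, 1% | 0.01 × 5 | 0.05 |
| One-off lapses, 5% | 0.05 × 5 | 0.25 |

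*95% CI half-width* = t(0.975, 63) × SD / √64. This is 2.00 at SD 8 and 3.00 at SD 12. The central shift is 0.23 / 3.00 = 7.8% to 0.23 / 2.00 = 11.7% of the half-width.

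**3. Would a same-state sensitivity model detect it?**

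Dropping subjects moves the mean by chance even without bias. The SD of the difference between the reduced and the full mean is SD × √(1/n₁ − 1/n).

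- Dropping 3 of 64: √(1/61 − 1/64) = 0.0277, so 0.22 (SD 8) to 0.33 (SD 12) points. The central bias of 0.23 is no larger than about one such SD.
- Dropping 6 of 64: √(1/58 − 1/64) = 0.0402, so 0.32 to 0.48 points. Only the extreme case, 0.94 points, would stand out.

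These use simple means with whole subjects removed. For a one-off lapse the mixed model still uses the subject's other visits, so the removal noise would be smaller, but the shift there is at most 0.25 points.

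**The case for a change.** The strongest case for acting does not rest on size. The protocol has sites record the state of each test, yet the analysis plan ignores it. The SAP plainly cares about comparability elsewhere, since it confines the main analysis to clinic spirometry and bars some screening values from the baseline. A count table and one extra model are cheap, leave the main estimates untouched, and would replace assumption with fact. Nor would any parent-study rule on baseline state stop a later one-off lapse from differing from a pre-bronchodilator baseline.

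Part of this stands. The SAP is silent on test state, and one-off lapses can enter the model. The protocol's reference to ppFEV₁ sensitivity analyses and the SAP's reply do not match well, and SAP 3.1 does not list the omission as a departure from the protocol. That is a general point about sensitivity analyses, however. It does not single out bronchodilator state, and the documents contain no figure showing that this variable matters more than others.

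The rest does not carry. The extra model would exclude bronchodilator users who failed to withhold, which changes the population as well as the measurement. It also needs the state of the parent-study baseline test in the analysis data, whereas the protocol promises only a source-document record for this study. Absence of a planned table does not mean that the information cannot surface: subject listings are planned, spirometry goes to a central service for quality review, and the list of potential important deviations in SAP 10.2.1.7 and 10.2.2.7 is open-ended.

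**Conclusion.** The description of the plan is accurate, but no change is needed. Whether the Part A Day 1 rule produces any mismatch cannot be determined without the parent study's rule. What remains is occasional one-off lapses, worth an assumed 0.05 to 0.25 points per visit at 5 points each. The central assumed case, 3 of 64 subjects mismatched by 5 points, shifts a visit mean by 0.23 points against a half-width of 2.0 to 3.0. The assumed range is 0.03 to 0.94, and shifts in opposite directions partly cancel.

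ppFEV₁ is a secondary endpoint, reported descriptively with confidence intervals and no multiplicity adjustment, so no test decision depends on a shift of this order. The additional model would leave the main estimate as it is and could not separate the central-case bias from the chance effect of dropping subjects.

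This rests on mismatches being few. If the state is in the analysis data, an analyst can count mismatched tests in passing, and look further only if the count is unexpectedly high. That is ordinary practice and needs no amendment.
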